## 1.0 OBJECTIVES

- 1.1 To compare molecular response rates with the FND regimen followed by rituximab (chimeric anti-CD20 antibody) and interferon versus FND plus rituximab concurrently, followed by interferon, for patients with stage IV indolent lymphoma.
- 1.2 To compare the toxicity of these two regimens, including their effects on B- and T-cell subsets, immunoglobulins, and patterns of infections.
- 1.3 To compare failure-free and overall survival rates with these two regimens.
- 1.4 To identify and treat with a separate strategy those follicular lymphoma patients without bcl-2 mbr or mcr gene rearrangement ("germline" patients) because of their adverse outcome with FND alone in our prior experience.

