## 5.0 TREATMENT PLAN

5.1. All patients must be registered with Data Management at [name]. They will be interviewed first by the Research Nurse before registration.

5.1.1 Follicular lymphoma patients who are known not to have bcl-2 gene rearrangement will not be randomized -- they will proceed directly to therapy with the ATT regimen (see Appendix B).

If there is no threatening disease and the clinician judges that it is safe to wait for the bcl-2 data, the initiation of therapy may be delayed (This is encouraged.)

However, if therapy is needed, it will not be delayed just for the bcl-2 report. If bcl-2 status is not known or pending, patients will be randomized. If, after therapy with FND begins, a patient is found to be germline for bcl-2, the patient will be crossed over to ATT (see strategy outline in Appendix B).

5.1.2 Randomization will be stratified for: tumor mass size < 5 cm vs. ≥ 5 cm; age < 60; FLC histology; SL histology; and suitability for the watch-and-wait policy followed at other institutions.

5.2 ARM 1 (delayed anti-CD20 arm) will consist of consecutive courses of Fludarabine/Mitoxantrone/Dexamethasone (FND), followed by rituximab.

Agent	Dose	Days	Route	Time	Total Dose
Fludarabine	25 mg/m 	1-3	IV	15 min	75 mg/m 
Mitoxantrone	10 mg/m 	1	IV	15 min	10 mg/m 
Decadron	20 mg	1-5	IV or PO	15 min	100 mg

5.2.1 Duration of therapy and intervals between courses:

- a) The courses should be repeated every 28 days according to recovery from myelosuppression.
- b) The total length of treatment will be 8 courses unless cumulative myelosuppression is encountered, in which case the treatment will be finished after 6 courses. Cumulative myelosuppression is defined as recovery of granulocytes to ≥ 1,000 or platelets to >100,000 requiring more than 6 weeks.

5.2.2 Patients older than 60 years will receive full doses of chemotherapy. Anyone experiencing delayed recovery of granulocyte counts (>35 days) or neutropenic fever will be candidates for G-CSF (Neupogen), with the chemotherapy doses adjusted down one dose level. The G-CSF dose will consist of 300 mcg total dose daily, subcutaneously. The dose can be increased to 480 mcg daily at the clinician's discretion.

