### 10.2 Accrual Rate:

The average yearly accrual rate during the past 4 years on the current low grade lymphoma stage IV clinical trial has been 33 patients per year. Previous experience at M.D. Anderson Hospital has shown that the PCR positivity rate in these stages is in the neighborhood of 60% when tested with the mbr probe only. If the mcr probe is added, approximately 75% of patients can be expected to have a positive PCR at the time of diagnosis. Accrual of the target 128 evaluable patient (see 10.3 e) will therefore take just over 5 years (estimated 5 years, 2 months). Allowing for some inevaluable cases (9% on protocol 88-050), a total accrual of about 185 patients is planned. [Amendment May 2001: Planned accrual changed to 210 patients, with restriction of eligibility to follicular lymphoma only for the last 25-30 patients, so that adequate numbers are entered to fulfill the goal outlined in 10.3.a below. This amendment results from higher-than-expected numbers of patients with small lymphocytic (including MALT) lymphoma being entered.]

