e. the FFS of patients in the concurrent arm is different from the delayed arm. This is the secondary efficacy endpoint for which we can expect information on a reasonable time frame. (For survival, long-term follow-up is intended, but mature data requires 5-10 years follow-up -- which serves to emphasize the need to identify reliable surrogate endpoints). A 3-year FFS of 50% with standard therapy is typical. Assuming one FND plus rituximab scheme matches this standard expectation, and the other exceeds it by 20%, the trial will have power of 0.66 to detect a difference of this size at significance level of 0.05. This assumes that 128 patients will be entered at the rate of two patients per month, that FFS is distributed exponentially, and that all patients will be followed for a minimum of one year. Nonetheless, this data will: (a) be an important endpoint to correlate with the molecular remission data; and (b) hopefully provide hypothesis-generating information for future, larger-scale trials.

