#### 10.4 Other Statistical Considerations

- a) Another secondary aim is to compare response rates, both CR (clinical CR plus CRu -- see Section 8.2) and CR + PR. It is anticipated to be high (approximately 80% CR and >90% CR + PR) in both arms; therefore it is unlikely that there will be significant differences between arms.
- b) Molecular response rates will be compared to CR and CR + PR rates.
- c) Other secondary aims, which are to compare the 5 year disease-free survival and overall survival for these 2 treatments, and to correlate the molecular complete remission rate with these endpoints, will require longer follow up. To attain these goals, we will follow the patients for at least 5 years to determine if a difference develops in disease-free survival. It might take 10 years or more of follow-up to establish statistically significant survival trends.
- d) Patients who are PCR negative will also be entered in this trial. These are of 2 categories: (a) "germline" follicular lymphoma; and (b) DSL (i.e., not follicular lymphoma).

Our preliminary data indicates that "germline" follicular patients have not done as well with FND as with ATT, so they will receive ATT, with rituximab. This will be a small number of patients (about 15% of follicular patients, i.e., about 16 patients on DM92-103), for whom analysis will be mainly descriptive. Likewise for DSL, which also will be a small subset of patients (24 in 4 1/2 years on DM92-103), traditional endpoints, including CR, PR, FFS, and survival will be used.

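### Does the failure-free survival comparison in 10.3e need a named population, a named test and a new power figure now that accrual is 210?

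*Combined protocol and SAP*

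**What the plan says.** Section 10.3e asks whether FFS differs between the concurrent and delayed arms. It takes 50% at three years as standard, supposes that one arm does 20 points better, and concludes that "the trial will have power of 0.66 to detect a difference of this size at significance level of 0.05". The inputs follow: "This assumes that 128 patients will be entered at the rate of two patients per month", exponential FFS, and at least one year of follow-up for everyone. The section then says that the data will be correlated with molecular remission and, it is hoped, will generate hypotheses for larger trials.

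Section 10.2 ties the same number to the molecular target: "Accrual of the target 128 evaluable patient (see 10.3 e) will therefore take just over 5 years (estimated 5 years, 2 months". The May 2001 amendment there reads "Planned accrual changed to 210 patients, with restriction of eligibility to follicular lymphoma only for the last 25-30 patients", and gives as its purpose the goal in 10.3a, the molecular endpoint.

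Other sections bear on who might be in an FFS comparison:

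- Objective 1.3 is unrestricted: "To compare failure-free and overall survival rates with these two regimens".
- Section 5.1.2 lists among the stratification factors "FLC histology; SL histology; and suitability for the watch-and-wait policy followed at other institutions", so SL patients are randomised.
- Section 5.1.1 randomises patients whose bcl-2 status is unknown. If, after FND has begun, "a patient is found to be germline for bcl-2, the patient will be crossed over to ATT".
- Section 10.4d names two PCR-negative categories, germline follicular and DSL (not follicular). It says that germline analysis will be mainly descriptive, treats DSL likewise as a small subset, and says that for DSL "traditional endpoints, including CR, PR, FFS, and survival will be used".

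**The concern.** FFS needs no PCR marker, so it can be measured in every randomised patient. The only power figure nevertheless uses the number of PCR-positive patients needed for a different endpoint, and it was left alone when accrual rose to 210. No section states whether randomised SL patients, or patients who crossed over to ATT, enter the between-arm comparison, and no test is named.

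If that is a real gap, two things are at stake. An analyst could choose between about 128 PCR-positive patients and a larger randomised set after seeing both results. A reader also could not tell how informative the comparison is for the trial as randomised.

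**Working it through.** **1. The plan's own figure.** Inputs from 10.3e: three-year FFS of 50% against 70%, 128 patients at 2 per month (64 months, 5.33 years), minimum follow-up 1 year. I assume 1:1 allocation (64 per arm, as in 10.3a), uniform entry and two-sided 0.05; 10.3e does not state the sidedness.

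- Hazards: ln 2 / 3 = 0.231 and −ln 0.7 / 3 = 0.119 per year. Hazard ratio (HR) = 0.515.
- Event probability with accrual A and minimum follow-up F: 1 − [exp(−λF) − exp(−λ(A+F))] / (λA). This gives 0.544 and 0.342.
- Events: 64 × 0.544 + 64 × 0.342 = 34.8 + 21.9 = 56.7.
- Freedman: √56.7 × (1 − 0.515)/(1 + 0.515) − 1.96 = 2.41 − 1.96, power 0.675.
- Schoenfeld: √56.7 × |ln 0.515| / 2 − 1.96 = 2.50 − 1.96, power 0.706.

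The stated 0.66 is within 0.02 of Freedman's value. It is not an arithmetic error.

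**2. Where 128 comes from.** Section 10.3a needs 64 PCR-positive patients per arm, so 128. Section 10.2 has 33 patients a year, 75% PCR-positive: 33 × 0.75 = 24.75 a year, or 2.06 a month, and 128 / 24.75 = 5.17 years. That matches the 5 years 2 months in 10.2 and the two per month in 10.3e. The FFS calculation therefore describes PCR-positive patients.

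**3. How large a randomised set might be.** The protocol does not give this, so I assume it.

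- SL share from 16% (24 patients in 4.5 years at 33 a year, 24/148.5) to 30%. Germline is 15% of follicular patients (10.4d).
- 16% SL: 210 × 0.84 × 0.85 + 210 × 0.16 = 184.
- 30% SL: 210 × 0.70 × 0.85 + 210 × 0.30 = 188.
- With 9% inevaluable also removed: 167 to 171.

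**4. Power for 167 to 188 patients.** One-year minimum follow-up, HR 0.515 for everyone. The protocol implies three accrual periods for the 210.

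| Accrual period | Basis | Events | Power (Freedman, N=167, to Schoenfeld, N=188) |
|---|---|---|---|
| 5.17 years | synopsis: a little over 5 years | 73–82 | 0.78–0.85 |
| 6.36 years | 210 at 33 a year | 80–90 | 0.82–0.88 |
| 8.75 years | 210 at 2 a month | 92–104 | 0.87–0.92 |

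**5. If SL patients do not share the effect.** Suppose the SL hazard is 0.231 in both arms, accrual takes 6.36 years, and the log-rank test is stratified by SL. With 28% SL and N=167:

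- Non-SL: 120.2 patients × 0.481 (the average of 0.584 and 0.377) = 57.8 events.
- SL: 46.8 × 0.584 = 27.3 events. Total 85.1.
- z = 57.8 × 0.3205 / √85.1 = 2.01, where 0.3205 = (1 − HR)/(1 + HR) from the unrounded HR. Power about 0.52.

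With N=188 the same steps give 65.0 and 30.7 events, z = 2.13 and power about 0.57. Over the same range of N, the working figures for this stratified test are 0.52 to 0.58 at 28% SL and 0.69 to 0.74 at 16% SL. The corresponding figure for 128 PCR-positive patients is about 0.69 by simulated log-rank.

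**6. What the amendment restores.** If the SL share is 28%, the follicular patients who are not germline number 210 × 0.72 × 0.85 = about 128. Raising accrual to 210 then brings the trial back to the 128 that 10.3e already uses.

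**The case for a change.** The case for a change is that 10.3e calls FFS the secondary efficacy endpoint on which information can be expected in a reasonable time, and objective 1.3 does not restrict it. Section 10.4d does not say that SL patients are left out of the arm comparison; it lists FFS among their endpoints. It also assumes a small SL subset, whereas the amendment records more SL patients than expected. It does not mention patients who have an assigned arm but then receive ATT. Depending on the set and the assumptions, power runs from about 0.52 to 0.92, and a few sentences would settle the matter.

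Part of this stands: the wording is silent on the set, the test and the crossovers. The inference that 0.66 describes the wrong population does not stand. Read with 10.2 and 10.4d, the natural sense is that 10.3e concerns the 128, with the two PCR-negative groups reported apart.

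The obvious remedy is not clearly an improvement either. Using all randomised patients who are not germline gains power if SL patients benefit equally, and loses it if a sizeable SL group does not. A new power figure would rest on an SL share and an accrual period that the protocol does not fix. The unspecified test matters little, because a log-rank comparison by assigned arm, stratified by the 5.1.2 factors, is the ordinary default for this design.

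The risk of choosing a set after the event is real in principle. It is limited here because no confirmatory claim rests on FFS, and reporting both sets side by side removes it.

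**Conclusion.** No change follows. The 0.66 is right for the inputs that 10.3e prints (0.675 to 0.706 on recalculation), and those inputs are openly the PCR-positive target. The section discloses the low power and confines FFS to correlation with molecular remission and to generating hypotheses. The amendment was made for the molecular endpoint, so it did not oblige a new FFS calculation.

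What is missing is detail that a competent analyst supplies: compare by assigned arm with a stratified log-rank test, show results by histology, and report with and without patients later found germline. Either candidate set, analysed that way, gives a valid comparison.

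The choice between them is a trade-off. Against about 0.66 to 0.71 for the 128, the larger set offers about 0.78 to 0.92 if the HR of 0.515 applies to everyone, and 0.52 to 0.58 if 28% are SL patients who gain nothing. These ranges rest on an assumed 167 to 188 patients, one-year minimum follow-up and exponential FFS, with accrual over 5.17 to 8.75 years for the common-HR range and 6.36 years for the SL range. The protocol gives no reason to expect that SL patients do not benefit; that scenario is included only to show that a larger set does not always have more power.

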#### 10.4 Other Statistical Considerations

- a) Another secondary aim is to compare response rates, both CR (clinical CR plus CRu -- see Section 8.2) and CR + PR. It is anticipated to be high (approximately 80% CR and >90% CR + PR) in both arms; therefore it is unlikely that there will be significant differences between arms.
- b) Molecular response rates will be compared to CR and CR + PR rates.
- c) Other secondary aims, which are to compare the 5 year disease-free survival and overall survival for these 2 treatments, and to correlate the molecular complete remission rate with these endpoints, will require longer follow up. To attain these goals, we will follow the patients for at least 5 years to determine if a difference develops in disease-free survival. It might take 10 years or more of follow-up to establish statistically significant survival trends.
- d) Patients who are PCR negative will also be entered in this trial. These are of 2 categories: (a) "germline" follicular lymphoma; and (b) DSL (i.e., not follicular lymphoma).

Our preliminary data indicates that "germline" follicular patients have not done as well with FND as with ATT, so they will receive ATT, with rituximab. This will be a small number of patients (about 15% of follicular patients, i.e., about 16 patients on DM92-103), for whom analysis will be mainly descriptive. Likewise for DSL, which also will be a small subset of patients (24 in 4 1/2 years on DM92-103), traditional endpoints, including CR, PR, FFS, and survival will be used.

## 11.0 DATA AND PROTOCOL MANAGEMENT

- 11.1 Protocol Compliance: The attending physician and oncology research nurse must see each patient at least every 2-3 cycles. All required interim and pretreatment data should be available and the physician must have made a designation as to tumor response and toxicity grade.
- 11.2 Data Entry: Data must be entered into the Clinical Data Management System. A brief explanation for required but missing data should be recorded as a comment.
- 11.3 Accuracy of Data Collection: The Study Chairman will be the final arbiter of response of toxicity should a difference of opinion exist.

## 12.0 REPORTING REQUIREMENTS

- 12.1 Any life-threatening and/or unexpected and serious (Grade 3 or 4) toxicity will be reported immediately to the Study Chairman who, in turn, must notify the Surveillance Committee and the sponsoring agency. Genentech [name] [contact] [name], [contact].

APPENDIX A  
 ACTIVITY FLOW CHART

	PRE STUDY	WEEKLY	EVERY 2 COURSES	EVERY 3 COURSES	EVERY 6 MONTHS	POST-THERAPY
H & P	X		X			q 3-6 mo
PS	X					
CBC	X	X				q 3-6 mo
U/A	X					
CXR	X					q 3-6 mo ‡
SMA 12, K, MG*	X		X			q 3-6 mo
B2M	X			X		q 3-6 mo
BX/FNA*	X					
BM BX	X			X		q 6 mo ‡
LAG, CTs	X			X		q 6 mo ‡
PB markers, Ig's	X			X***		
PB PCR	X				X**	
BM PCR	X				X**	
ECHO or MUGA	X					

♣ K, Mg, etc as indicated, mainly for pts on ATT (see App. B)

\* when accessible; for phenotype, gene rearrangement

\*\* PCR for bcl-2 q 6 mo yr 1-3, q 12 mo thereafter. Contingency for PCR monitoring at 9 and/or 15 months for selected patients (see 7.2)

\*\*\* PB markers, Ig's: until recovery to normal

‡ Restaging off therapy (see section 7.7): at least q 6 mo until relapse or through year 5; then at least yearly.

## APPENDIX B

### MANAGEMENT STRATEGY FOR FOLLICULAR LYMPHOMA PATIENTS WHO DO NOT HAVE BCL-2 MBR OR MCR GENE REARRANGEMENT ("GERMLINE" PATIENTS).

- I. Since these patients appear to have an inferior outcome with FND compared courses to ATT, these patients will receive ATT, 9 courses total, and all will also receive rituximab, 6 doses total. This will include d.1 and 8 doses of rituximab during the first cycles of CHOD-Bleo and NOPP (but not ESHAP) courses, and d.1 only during the second cycles of CHOD-Bleo and NOPP.

All "germline" patients will also receive interferon maintenance, as outlined for FND + rituximab patients (see 5.7).

Since the bcl-2 status may not be available prior to starting therapy, some will have received one (or rarely two) cycles of FND, with or without rituximab, prior to crossover to ATT. In such cases, the final chemotherapy cycle of the ATT sequence (NOPP) will be omitted, so that the total number of chemotherapy cycles is nine.

If the patient had been randomized to receive FND + rituximab and thus already received doses of rituximab, the subsequent courses of ATT, with d.1 and 8 IDEC during each CHOD-Bleo and NOPP course, should complete all 6 planned doses of rituximab (see scenario B below). For any patient who does not complete nine courses of chemotherapy, any missed doses of rituximab can be completed after the last chemotherapy cycle.

If the patient had been randomized to receive FND without rituximab, see scenario C.

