#### Scenarios:

A. When the bcl-2 status is known before therapy (i.e., those patients who are not randomized -- see section 5.1.1):

- course 1: CHOD-Bleo, plus rituximab d. 1 & 8
- course 2: ESHAP
- course 3: NOPP, plus rituximab d.1 & 8
- course 4: CHOD-Bleo, plus rituximab d.1 only
- course 5: ESHAP
- course 6: NOPP, plus rituximab d.1 only
- courses 7-9: CHOD-Bleo; ESHAP; NOPP (No more rituximab)

B. If patient had been randomized, and got FND with rituximab:

- course 1: FND + rituximab d. 1 & 8
- course 2: CHOD-Bleo, plus rituximab d.1 & 8
- course 3: ESHAP
- course 4: NOPP, plus rituximab d.1 & 8
- course 5: CHOD-Bleo without rituximab
- course 6: ESHAP
- courses 7-9: NOPP; CHOD-Bleo; ESHAP (No more rituximab)

C. If patient had been randomized, and got FND without rituximab:

- course 1: FND
- course 2: CHOD-Bleo, plus rituximab d. 1 & 8
- course 3: ESHAP
- course 4: NOPP, plus rituximab d. 1 & 8
- course 5: CHOD-Bleo, plus rituximab d. 1 & 8
- course 6: ESHAP
- courses 7-9: NOPP; CHOD-Bleo; ESHAP (no more rituximab)

For any questions about this sequence, consult P.I.

For all cycles given in conjunction with rituximab, the steroid will start on d. 1 along with the rituximab, and the remainder of the chemotherapy will start one day later than standard, analogous to the modified schedule of FND as outlined in Section 5.

II. ATT doses and schedule (with rituximab in CHOD-Bleo and NOPP courses):

1. Initial Dosing Regimen for CHOD-Bleo:

Agent	Dose	Days	Route	Time	Total Dose
Rituximab	375 mg/m 	1 & 8	IV	approx 4 hr (Sec 5. 4)	750 mg/m 
Adriamycin	25 mg/m  /day	2-3	IV-CI	48 hrs	50mg/m 
Oncovin	0.7 mg/m  /day	2-3	IV-CI	48 hrs	1.4 mg/m 
Bleomycin	5 u/m  /day	2-3	IV-CI	48 hrs	10 u/m 
Cytosan	750 mg/m 	2	IVPB	15 min	750 mg/m 
Dexamethasone	40 mg/day	1-4	p.o.	--	160 mg

2. Initial Dosing Regimen for ESHAP:

Agent	Dose	Days	Route	Time	Total Dose
Etoposide	40 mg/m  (daily)	1-4	IV	30 min	160 mg/m 
Cisplatin	25 mg/m  (daily)	1-4	IV-CI	96 hrs	100 mg/m 
Ara-C	1.5 gm/m  (single dose)	5	IV	2 hrs	1.5 gm/m 
Solu Medrol	500 mg (daily)	1-5	IV	15 min	2500 mg

3. Initial Dosing Regimen for NOPP:

Agent	Dose	Days	Route	Time	Total Dose
Rituximab	375 mg/m 	1 & 8	IV	approx 4 hr (Sec 5.4)	750 mg/m 

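### Appendix B's crossover rule gives ten chemotherapy cycles, not the stated nine, when a germline patient has already had two FND cycles

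*Combined protocol and SAP*

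**What the plan says.** Appendix B, part I, sets the standard for germline patients: "these patients will receive ATT, 9 courses total, and all will also receive rituximab, 6 doses total". Because the bcl-2 result can arrive after treatment has begun, it adds that "some will have received one (or rarely two) cycles of FND, with or without rituximab, prior to crossover to ATT". The next sentence refers back to all of those patients and gives one instruction: "the final chemotherapy cycle of the ATT sequence (NOPP) will be omitted, so that the total number of chemotherapy cycles is nine".

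The scenarios that follow in Appendix B work through three sequences. Scenario A has no prior FND and runs to nine ATT courses, the ninth being NOPP. Scenarios B and C each begin with one FND course, with and without rituximab respectively, and continue with eight ATT courses. Scenario B, for example, ends "courses 7-9: NOPP; CHOD-Bleo; ESHAP (No more rituximab"). No scenario starts with two FND courses. Below them stands a general fallback: "For any questions about this sequence, consult P.I".

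**The concern.** The instruction covers two groups, patients with one prior FND cycle and patients with two, but prescribes the same single omission for both and claims the same total for both. A fixed omission cannot offset a variable number of earlier cycles, so the stated total can be right for only one group.

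This is an operative treatment rule, not background. After two FND cycles a treating physician cannot satisfy both halves of the sentence. Omitting only the final NOPP exceeds nine cycles; holding to nine means omitting a second ATT course that the text does not name. If courses are trimmed from the end, the surplus course is the third ESHAP, which by the dosing table in Appendix B, part II, carries cisplatin 100 mg/m² and Ara-C 1.5 g/m².

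**Working it through.** **Inputs (all from Appendix B, except Arm 2 dosing from Section 5.3)**

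- Full ATT: 9 courses, CHOD-Bleo, ESHAP, NOPP repeated three times (part I and scenario A).
- FND cycles before crossover: 1, rarely 2 (part I).
- ATT courses omitted at crossover: 1, the final NOPP (part I).
- Stated total: 9 (part I).

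**Cycle count as written**

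Total = FND cycles given + (9 − 1).

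| Prior FND cycles | ATT courses left | Total | Stated total |
|---|---|---|---|
| 1 | 9 − 1 = 8 | 1 + 8 = 9 | 9 |
| 2 | 9 − 1 = 8 | 2 + 8 = 10 | 9 |

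The first row reproduces the plan's figure and matches scenarios B and C course by course. The second row does not reproduce it. The count does not depend on the randomized arm.

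**Cycle count with one omission per FND cycle**

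Total = k + (9 − k) = 9 for any number k of FND cycles. For k = 1 the final NOPP is dropped: 1 + 8 = 9. For k = 2 the final ESHAP and NOPP are dropped: 2 + 7 = 9. The seven remaining courses are CHOD-Bleo, ESHAP, NOPP, CHOD-Bleo, ESHAP, NOPP, CHOD-Bleo.

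**Do six rituximab doses still fit after two FND cycles?**

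- Arm 1 (no rituximab yet): 2 with ATT course 1, 2 with ATT course 3 and 2 with ATT course 4 give 0 + 2 + 2 + 2 = 6. These are the same ATT courses as in scenario C, where the last pair falls at "course 5: CHOD-Bleo, plus rituximab d. 1 & 8".
- Arm 2: Section 5.3 gives days 1 and 8 in course 1 and day 1 in course 2, so 2 + 1 = 3 doses precede ATT. For patients who have already had rituximab, Appendix B calls for days 1 and 8 with each CHOD-Bleo and NOPP course. Followed literally, the first CHOD-Bleo brings the count to 3 + 2 = 5 and the first NOPP to 5 + 2 = 7, one above the planned six. Giving day 1 only with that NOPP yields 3 + 2 + 1 = 6.

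Scenario B does not meet this problem. With one FND-rituximab course the count is 2 + 2 + 2 = 6 by the first NOPP, and rituximab then stops ("course 5: CHOD-Bleo without rituximab").

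**The case against.** The best reply is that nobody would be misled. The purpose clause names nine, full ATT is nine courses, the following paragraph again uses nine courses as its benchmark, and every scenario stops at course nine. On that reading a physician continues the scenario B or C order and stops at nine, which drops the final ESHAP and NOPP, the same result as the fix below. Anyone in doubt is told to ask the principal investigator.

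The reach is also very small. The patient must be germline (about 15% of follicular patients, Section 10.4 d), must have started with bcl-2 status unknown although Section 5.1.1 encourages waiting when that is safe, and must still have no result when a second FND course is given. There may be no such patient. Germline analysis is mainly descriptive, and the primary endpoint is defined for patients with an initially positive PCR (Section 8.2).

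Finally, the rituximab schedule for the Arm 2 case is one way of giving the last three doses, and the documents do not select it; the six-dose total is already stated.

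Most of this stands, and it limits the severity. It does not remove the conflict. The explicit action in the sentence is to omit one named course, and a physician who does so may see no question to ask. The intention is clear only from the half of the sentence that the instruction contradicts. As for rituximab, the six-dose total and the instruction for days 1 and 8 with each course also collide after two FND-rituximab cycles, so a clarifying sentence is useful. Which doses and which ATT course to drop remain clinical choices.

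**Conclusion.** The point holds and is minor. For a patient who crosses over after two FND cycles, in either arm, the rule as written gives ten chemotherapy cycles against a stated nine: one course too many. For the usual one-cycle crossover the stated total is correct.

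This rests on two readings. The omission sentence applies to both groups named just before it, and exactly one ATT course is omitted, as stated. The documents do not give the number of patients affected and describe the situation as rare. Neither the randomized primary comparison nor the sample size is affected.

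**What to change.** Replace the sentence in Appendix B, part I, with a rule that one ATT course is omitted from the end of the sequence for each FND cycle already given: after one, the final NOPP; after two, the final ESHAP and NOPP, or another course that the investigator names. The total then stays at nine.

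Add one sentence saying that rituximab stops at six doses in total, counting doses given with FND. For an Arm 2 patient with two prior FND-rituximab cycles, a workable schedule is days 1 and 8 with the first CHOD-Bleo and day 1 only with the first NOPP.

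The cost is one corrected and one added sentence, with no change to design, sample size or analysis. The clinical downside is seven rather than eight ATT courses in a rare case, for patients in whom the background (Section 2.4) regards an intensive regimen such as ATT as important. The stated total of nine already implies that reduction. If the sponsor prefers to keep eight ATT courses, the appendix should instead state ten cycles for this case.
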